1 BACKGROUND AND OVERVIEW OF CLINICAL STUDIES

Increasing physical activity levels may improve cardiovascular health and BP levels in young individuals, especially if such strategies promote healthy lifestyles. Physical activity is currently recommended for adults CV health, but physical activity levels are known to be low in populations with diabetes or chronic kidney disease.^{5,6,7,8} One prior study of the use of pedometers (not associated with wireless technology or provider feedback) in children with CKD did not significantly improve physical activity levels.⁹ Supervised walking appeared to provide some benefit in individuals with type II diabetes, but overall compliance was poor.^{9,10} Interview of adolescents and young adults with chronic illnesses has shown preference for the use of electronic devices and online tools for disease management.^{11,12} Thus, use of sophisticated electronic devices such as FitBits[©] (wireless pedometers worn on the wrist that sync with cell phones) may improve disease control by engaging young patients in self-monitoring of their own health and lifestyle behaviors. FitBits[©] have been previously validated in clinical studies for the accuracy of step count.¹³

PROTOCOL SYNOPSIS

TITLE	Physical Activity Trackers to Blood Pressure (PAT-BP)
SPONSOR	NIH
FUNDING ORGANIZATION	NHLBI
NUMBER OF SITES	1
RATIONALE	The rationale for this study is to determine whether use of physical activity trackers (Fitbits) helps improving patient self-awareness of their fitness level and enhance healthy lifestyle changes that may lead to lower blood pressure. The potential benefits (increased walking on a daily basis and awareness of own fitness level) outweigh the risks in this study (anxiety about step count, minimal risk of loss of confidentiality).
STUDY DESIGN	
This is a pilot randomized controlled trial.
 
We will recruit 75 adolescents and young adults at UCSF. Patients included for study will be between ages 8-30 receiving anti-hypertensive therapy at the time of recruitment or have elevated BP > 120 mm Hg or > 95th percentile for age/sex/height if < 18 years of age.^{14,15}
 
Study intervention. Daily use of physical activity tracker coupled with biweekly provider telemonitoring and feedback (via secure email, phone call, or text) will be compared to usual care (daily use of physical activity tracker with biweekly feedback for the latter 6 months of the study). The study intervention will last 6 months for patients in the usual care group and 12 months for patients in the intervention group. Physical activity and data will be reviewed by telemonitoring on a biweekly basis by study personnel. Patients will receive feedback on their progress from study personnel via patient-preferred communication modalities (secure e-mail, phone call, or text) biweekly. If daily step count is below desired goal (as per age-appropriate references),¹⁶ patients will be provided with ideas on how to increase physical activity level/step counts (e.g. parking further from their destination and walking, taking stairs instead of elevator).

OBJECTIVES	
To determine feasibility of a randomized controlled trial testing to effect of physical activity trackers on blood pressure levels.
 
To determine potential effect sizes from the use of physical activity trackers on change in blood pressure.

NUMBER OF SUBJECTS	75

SUBJECT SELECTION CRITERIA	
Inclusion Criteria:
 
Patients included for study will be
 
 • Male or female between ages 8-30 receiving anti-hypertensive therapy at the time of recruitment. We will target patients with DM, non-dialysis requiring CKD, or kidney transplant, but will not exclude patients with other etiologies of hypertension who are deemed eligible (such as fibromuscular dysplasia). • Only patients with phones compatible for wireless device data transmission will be eligible. Wireless sync between Fitbit monitors and online account (provided by Fitbit which securely stores step count) will be set-up in clinic, and only patients who consent to grant study personnel access to home monitoring data will be enrolled. • Written informed consent (and assent when applicable) obtained from subject or subject's legal representative and ability for subject to comply with the requirements of the study. 
Exclusion Criteria: We will exclude patients with a history of decompensated congestive heart failure, pregnancy, cognitive impairment (and therefore inability to self-manage disease), non-ambulatory patients who are unable to perform physical activity, patients with BP >180/110 mm Hg, prisoners, patients with any contraindication to use or wear of home activity tracker (such as allergy to activity tracker band), or presence of any co-morbidity that would preclude physical activity (such as moderate or severe cerebral palsy).

TEST PRODUCT, DOSE, AND ROUTE OF ADMINISTRATION	
1.1 Fitbit (to be worn on the wrist).
 
Up to 75 eligible patients will be randomly assigned to Fitbit or usual care treatment groups in a 2:1 ratio using a randomization scheme developed by the study data management provider. Due to the objectives of the study, the identity of test and control treatments will be known to investigators, patients.

CONTROL ARM	
Usual care is defined as routine clinical care for the first 6 months of the study and wearing a Fitbit for the last 6 months of the study.

STATISTICS**Primary Analysis Plan**

The primary feasibility outcomes will be tallied using simple proportions and descriptive statistics. Chi-square and other tests will be used to characterize participants who did and did not enroll. To examine differences in clinical outcomes, intention-to-treat analysis will be performed. Change in mean office systolic BP between 3 and 12 months, compared across usual care vs. intervention arms will be evaluated using t-tests and mixed linear models with an interaction term between time and randomization arm to evaluate change in office BPs at various time intervals both between groups and within-subjects.

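### Treated patients can enter at any BP up to the 180/110 exclusion, and neither the stated allocation nor the pooled BP comparison takes account of entry BP

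*Combined protocol and SAP*

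**What the plan says.** All references are to the Protocol Synopsis and the Statistics section of the combined protocol and SAP.

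- **Subject Selection Criteria.** The inclusion list has one BP-related entry route: "Male or female between ages 8-30 receiving anti-hypertensive therapy at the time of recruitment". It sets no minimum BP. The only BP limit that reaches these patients is the exclusion of "patients with BP >180/110 mm Hg".
- **Study Design.** This row joins two routes with an *or*: "receiving anti-hypertensive therapy at the time of recruitment or have elevated BP > 120 mm Hg or > 95th percentile for age/sex/height if < 18". The BP threshold belongs to the second route only. That second route does not appear in the inclusion list.
- **Test Product (randomisation).** Allocation is "in a 2:1 ratio using a randomization scheme developed by the study data management provider". No stratification factor is named.
- **Objectives.** The second objective is "To determine potential effect sizes from the use of physical activity trackers on change in blood pressure". It does not name a population by BP.
- **Statistics, Primary Analysis Plan.** Feasibility is primary. Office systolic BP is compared between arms by intention to treat, with t-tests and a mixed model containing a time-by-arm interaction. No term for entry BP, entry route or treatment status is listed, and no analysis by any of them.

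**The concern.** Under either statement of the criteria, the sample can mix patients whose BP is already controlled with patients whose BP is elevated. By the inclusion list alone, everyone is treated and the mix is of controlled and uncontrolled BP. By the Study Design row, untreated patients with elevated BP are added.

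Two things could depend on entry BP: the effect of the tracker, and the change in BP that would occur without it (through regression to the mean, for example). If the first does, the pooled effect reflects who attended this one site, and a small pooled effect could mean either a weak intervention or a largely controlled sample. If the second does, a chance difference between arms in entry BP adds noise to the arm difference. The plan as written has nothing that would separate these explanations or remove that noise.

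**Working it through.** **Inputs from the documents:** 75 patients at most and 2:1 allocation, so 50 tracker and 25 usual care. The documents give no SD, effect size, power or share with elevated BP, so there is no stated figure to reproduce. Everything marked *assumed* below is illustrative.

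**1. Chance imbalance without stratification.** *Assumed:* 38 of 75 have elevated BP. The number X falling in usual care is hypergeometric (75, 38, 25).
- Mean = 25 × 38/75 = 12.7.
- SD = sqrt(25 × 38/75 × 37/75 × 50/74) = 2.05.
- 95% range of X: 9 to 17. At X = 9 the shares are 9/25 = 36% in usual care and 29/50 = 58% in the tracker arm. At X = 17 they are 17/25 = 68% and 21/50 = 42%.
- SD of the arm difference in share = 2.05 × (1/25 + 1/50) = 0.123, about 12 percentage points.

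**2. What that imbalance is worth.** *Assumed:* change without the tracker differs by 5 mm Hg between elevated and non-elevated patients, and the SD of change is 10 mm Hg.
- Typical shift in the arm difference = 0.123 × 5 = 0.6 mm Hg.
- SE of the pooled arm difference = 10 × sqrt(1/50 + 1/25) = 10 × 0.245 = 2.45 mm Hg.
- Share of the sampling variance = (0.6/2.45)² = about 6%.

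**3. Dependence of the pooled effect on case mix.** *Assumed:* effect 5 mm Hg in elevated-BP patients and f × 5 in the rest, with e the share elevated. Pooled effect = 5 × (e + (1 − e) × f), in mm Hg:

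| f | e = 30% | e = 50% | e = 70% |
|---|---|---|---|
| 0 | 1.5 | 2.5 | 3.5 |
| 0.5 | 3.25 | 3.75 | 4.25 |
| 1 | 5 | 5 | 5 |

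The bottom row shows that case mix has no influence if the effect does not vary with entry BP.

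**4. Precision of results by entry BP status.** With about 25 and 12 patients in a stratum, SE = sqrt(1/25 + 1/12) × SD = 0.35 × SD, against 0.245 × SD pooled. At an assumed SD of 10, the 95% half-widths are 1.96 × 3.51 = 6.9 and 1.96 × 2.45 = 4.8 mm Hg.

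**5. Which estimate is closer to the elevated-BP effect?** Root mean squared error at SD 10 and e = 50%:
- Pooled, f = 0: sqrt((5 − 2.5)² + 2.45²) = 3.50.
- Pooled, f = 0.5: sqrt((5 − 3.75)² + 2.45²) = 2.75.
- Elevated stratum alone: 10 × sqrt(0.06/0.5) = 3.46.

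Even with no effect at all in the other patients, the two are about equal. With half the effect in the others, the pooled value is better. This argues against replacing the pooled estimate with the stratum estimate.

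**The case against.** This is a pilot with feasibility as its primary outcome, and broad entry looks deliberate: the plan "will not exclude patients with other etiologies of hypertension who are deemed eligible". Randomisation gives an unbiased average effect for whoever is enrolled, and the objective asks only for potential effect sizes. All of this stands. It limits the point to the second objective and rules out any claim that the comparison is invalid.

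The imbalance is part of ordinary sampling error and, on the assumptions above, worth about 0.6 mm Hg. That also stands: the gain from dealing with it is modest, but so is the cost.

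The randomisation scheme is left to the data management provider and not described. Stratification is therefore unstated, not ruled out. Even if the scheme does stratify, the analysis still lists no entry-BP term.

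The mixed model may include the entry measurement among its repeated outcomes, so that time by arm compares changes from entry. The plan does not say so, and that term would still not show whether the effect varies with entry BP.

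A reader might infer that a definitive trial sized on the pooled value would be far too large. Using (5/pooled effect)², the ratio is 11, 4 or 2 at f = 0 for 30%, 50% or 70% elevated, and 2.4, 1.8 or 1.4 at f = 0.5. The documents do not support that conclusion. The effects and shares are assumed, the ratio is 1 at f = 1, and the calculation presumes a later trial confined to elevated-BP patients, which the documents nowhere mention. For a later trial with the same criteria and a similar mix, the pooled value is the right input.

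**Conclusion.** The point holds as a matter of design and reporting. The text admits treated patients at any BP up to 180/110, names no stratification factor, and plans one pooled comparison without entry BP, while an effect size for BP change is an objective. The pooled estimate is unbiased for the mix enrolled. It becomes hard to carry to another mix only if the effect varies with entry BP, and it loses precision to imbalance only if the change without the tracker depends on entry BP.

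The one quantity that needs no assumption about effects is the imbalance: an SD of about 12 percentage points in the share elevated, given an assumed 38 of 75. The documents give no figure for the dilution, and it may be zero. They do not support a reading that the BP result is biased, or that the effect size must come from the elevated-BP patients alone.

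Separately, the Study Design row and the inclusion list disagree on whether elevated BP without treatment is an entry route. They must be reconciled.

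**What to change.** 1. Reconcile the Study Design row and the inclusion list on the elevated-BP route. Otherwise leave eligibility as it is.
2. Stratify the 2:1 randomisation by entry BP status (elevated or not), using the plan's own definition once reconciled, and state this in the randomisation text.
3. Add entry systolic BP to the Primary Analysis Plan's model as a continuous covariate. Say whether the entry measurement is also among the repeated outcomes, so that it is not used twice.
4. Keep the pooled adjusted arm difference with its 95% CI as the main effect size.
5. Report the arm difference with 95% CI by entry BP status, or an entry-BP-by-arm term, as descriptive only. Tabulate entry BP status by arm so that readers can see the mix.

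**Cost:** one stratification factor, one covariate and a few table rows. Entry BP is already needed for every patient to apply the BP exclusion. The stratum estimates will be imprecise (SE about 0.35 × SD against 0.245 × SD pooled), which is why they should not replace the pooled value. Stratification cannot be added for patients already randomised, but items 3 to 5 need no change to the allocation.

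### The one BP interval named for the between-arm test (months 3 to 12) runs past the month-6 start of the tracker in usual care, and no contrast within months 0 to 6 is designated as the BP effect estimate

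*Combined protocol and SAP*

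**What the plan says.** The synopsis of the combined protocol and SAP describes the trial under STUDY DESIGN: "This is a pilot randomized controlled trial". The two arms receive the tracker for different lengths of time: "The study intervention will last 6 months for patients in the usual care group and 12 months for patients in the intervention group". The CONTROL ARM row fixes when usual care gets it: "Usual care is defined as routine clinical care for the first 6 months of the study and wearing a Fitbit for the last 6 months". STUDY DESIGN adds feedback to that second half, describing usual care as "daily use of physical activity tracker with biweekly feedback for the latter 6 months of the study".

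Of the two OBJECTIVES, the first is feasibility. The second is "To determine potential effect sizes from the use of physical activity trackers on change in blood pressure".

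Under STATISTICS, Primary Analysis Plan, the feasibility outcomes are the ones called primary. For BP, the plan states: "Change in mean office systolic BP between 3 and 12 months, compared across usual care vs. intervention arms will be evaluated using t-tests". The same sentence adds "mixed linear models with an interaction term between time and randomization arm to evaluate change in office BPs at various time intervals", without listing the intervals. Neither baseline nor month 6 is mentioned. Clinical outcomes are to be analysed by intention to treat.

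**The concern.** Randomisation separates tracker from no tracker only until month 6. After that both arms wear it. The named interval of months 3 to 12 can be read in two ways.

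- **As a change from month 3 to month 12.** It starts when the intervention arm has already had 3 months of treatment and ends when usual care has had 6. Of its 9 months, 3 compare tracker with no tracker and 6 compare tracker with tracker.
- **As change from baseline at visits falling in months 3 to 12.** Contrasts up to month 6 are then sound, month 12 compares immediate with delayed start, and nothing says which visit supplies the estimate.

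What is at stake is the second objective. A pilot's BP effect size is likely to be carried into the planning of a later trial. On the first reading, that figure could be null or have the wrong sign for a tracker that works.

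**Working it through.** The plan gives no BP effect size, SD, power or onset pattern, so it has no figure of its own to reproduce. The check is algebraic.

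**Inputs from the documents.** Intervention arm: tracker from month 0 to 12 (STUDY DESIGN). Usual care: no tracker in months 0 to 6, tracker in months 6 to 12 (STUDY DESIGN, CONTROL ARM). Named interval: months 3 and 12 (Primary Analysis Plan).

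**Assumed inputs.**
- D is the full reduction in systolic BP, with positive values meaning benefit.
- f(t) is the share of D reached after t months on the tracker, with the same shape in both arms.
- r is usual care's response after month 6 relative to the intervention arm's. STUDY DESIGN gives usual care the tracker plus feedback, which fits r near 1. CONTROL ARM mentions only the device, so a lower r is possible. The range shown is 1, 0.5 and 0.

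**Formulas.** The arm difference in benefit is D·f(t) up to month 6 and D[f(t) - r·f(t-6)] after it.
- At month 3: D·f(3)
- At month 6, before the switch: D·f(6)
- At month 12: D[f(12) - r·f(6)]
- Literal contrast, month 12 minus month 3: D[f(12) - f(3) - r·f(6)]

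**Results, in units of D:**

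| Pattern: f(3), f(6), f(12) | Literal, r = 1 | r = 0.5 | r = 0 | Baseline to month 6 |
|---|---|---|---|---|
| Complete by month 3, sustained: 1, 1, 1 | 1 - 1 - 1 = -1.0 | -0.5 | 0 | 1.0 |
| Linear to month 6, then flat: 0.5, 1, 1 | 1 - 0.5 - 1 = -0.5 | 0 | +0.5 | 1.0 |
| Linear to month 12: 0.25, 0.5, 1 | 1 - 0.25 - 0.5 = +0.25 | +0.5 | +0.75 | 0.5 |
| Nothing until after month 6: 0, 0, 1 | 1 - 0 - 0 = +1.0 | +1.0 | +1.0 | 0 |

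A negative figure means that a working tracker looks harmful. The literal contrast is zero when r = [f(12) - f(3)]/f(6). That is r = 0, 0.5 and 1.5 for the first three patterns, so the third stays positive for any r up to 1. The literal contrast equals the month-6 effect only if f(12) - f(3) = (1 + r)·f(6). Nothing in the documents supports that condition in general.

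**Second reading, baseline to month 12.** D[f(12) - r·f(6)] at r = 1 gives 0, 0, 0.5D and 1.0D for the four patterns. The sign is not reversed in these cases, but an effect that has levelled off by month 6 shows as zero.

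The signs of these expected contrasts need no assumption about SD, sample size or dropout. They do depend on f and r.

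**The case against.** The best defence is that the literal reading may not be the one intended. The sentence goes on to look "at various time intervals both between groups and within-subjects", and that plural fits a range of follow-up visits. On that reading the month-3 and month-6 contrasts from baseline are valid. The planned mixed model could also supply the month-6 contrast on either reading, provided BP is measured then. This stands: the model is under-specified, not wrong. It does not settle the matter, because the plan never says which contrast is the effect estimate.

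A second defence is that the comparator is defined as delayed start, so baseline to month 12 is a legitimate randomised comparison of immediate with delayed start. This also stands. It does not rescue a starting value taken 3 months into treatment. Nor does intention to treat, which fixes who is analysed in which arm and not which interval is compared.

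Third, this is a pilot whose primary outcomes concern feasibility. That limits the consequence to one of two stated objectives but does not remove it.

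A reader might infer more than the documents allow:
- **That the BP analysis is bound to give a wrong answer.** The interval is ambiguous, and the mixed model leaves valid contrasts available.
- **That no BP comparison is named on any reading.** Taken literally, one is named (month 12 minus month 3). What is missing is one inside months 0 to 6.
- **That month 6 is always the better choice.** The last row of the table shows the opposite if the effect emerges late.

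**Conclusion.** The point holds in this form: the only interval named for the between-arm BP test extends 6 months past the end of the randomised tracker-versus-no-tracker period, and no contrast within that period is designated as the effect estimate.

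On the literal reading with r = 1, the expected result is -1.0D, -0.5D or +0.25D for effects complete by month 3, linear to month 6, or linear to month 12. The corresponding month-6 effects are 1.0D, 1.0D and 0.5D. A lower r reduces or removes the reversal, and a purely late effect is recovered in full by the literal contrast and missed at month 6. On the visit-range reading, the fault is only that no visit is singled out.

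The size rests wholly on assumed onset patterns and on r. That the literal contrast is not a tracker-versus-no-tracker comparison rests on the documents alone. The point should be fixed before BP effect sizes are reported. The feasibility outcomes are unaffected.

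**What to change.** In the Primary Analysis Plan, replace the months 3 to 12 interval with one named BP effect estimate: the between-arm difference in change in office systolic BP from baseline to month 6, using the last measurement before usual care starts the tracker. Take it from the planned mixed model, with visit as a categorical factor.

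Report the baseline-to-month-12 difference separately, labelled as immediate versus delayed start. Describe months 6 to 12 as durability in the intervention arm and delayed-start response in usual care.

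The cost is wording only, with no added patients, if an existing visit gives an office BP at month 6 before the switch. The sponsor must confirm this: Appendix 1 is an example schedule of five visits with the months left blank and no separate BP row, so it neither shows nor excludes such a measurement. The price of the change is that an effect emerging only after month 6 would not appear in the named estimate, which is why the month-12 comparison should still be reported.

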APPENDIX 1. EXAMPLE OF SCHEDULE OF STUDY VISITS

	VISIT 1 (Day/Week/Month #) ^a	VISIT 2 (Day/Week/Month #) ^a	VISIT 3 (Day/Week/Month #) ^a	VISIT 4 (Day/Week/Month #) ^a	VISIT 5 (Day/Week/Month #)
Informed Consent	X				
Medical History	X				
Complete Physical Exam	X				X
Abbreviated Physical Exam		X	X	X	
Height	X	X	X	X	X
Weight	X	X	X	X	X
Randomization	X				
Quality of Health Survey ^b	X		X		X
Initiate Subject Diary	X				
Subject Diary Review		X	X	X	X
Adverse Experiences	X	X	X	X	X

^a ±2 day

^b The Quality of Health Survey may be administered over the phone or email if needed.

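### The SBP comparison does not name the reference visit for change and has no baseline SBP term; if change is from entry, adjustment would modestly narrow the effect-size interval

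*Combined protocol and SAP*

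**What the plan says.** The Primary Analysis Plan defines the clinical comparison in one sentence. The outcome is "Change in mean office systolic BP between 3 and 12 months, compared across usual care vs. intervention arms". The method follows: it "will be evaluated using t-tests and mixed linear models with an interaction term between time and randomization arm", the purpose being "to evaluate change in office BPs at various time intervals both between groups and within-subjects". No reference visit is named, the intervals are not listed, and no baseline SBP covariate or common entry mean is mentioned.

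Other parts of the document bear on this:

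- **Objectives.** The second objective is "To determine potential effect sizes from the use of physical activity trackers on change in blood pressure".
- **Test Product.** Up to 75 patients "will be randomly assigned to Fitbit or usual care treatment groups in a 2:1 ratio", which is 50 versus 25 if all are enrolled.
- **Control Arm.** "Usual care is defined as routine clinical care for the first 6 months of the study"; these patients then wear the tracker for the remaining 6 months.
- **Subject Selection Criteria.** The exclusions include "patients with BP >180/110 mm Hg", so a BP value is needed before entry.
- **Appendix 1** ("EXAMPLE OF SCHEDULE OF STUDY VISITS"). Randomization is marked at Visit 1 only. The visits carry no month numbers and the table has no BP row.

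**The concern.** There are two linked problems.

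**Outcome definition.** The 3-to-12-month wording can mean change from entry, assessed at visits from month 3 to month 12, or it can mean month 12 minus month 3. These are different quantities. Month 3 falls after randomisation, so the second omits any effect that arises before month 3. Two analysts could follow the sentence faithfully and report different effect sizes.

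**Precision.** If change is from entry, a t-test on change fixes the coefficient of entry SBP at 1. A time-by-arm model that leaves the entry means free gives the same contrast when data are complete. ANCOVA estimates the coefficient instead, and a model with a common entry mean recovers essentially the same gain. Under randomisation all of these are unbiased, but the adjusted ones usually give a narrower interval.

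What is at stake is the width of the effect-size interval, in a pilot where that estimate is one of two objectives and comes from at most 75 patients.

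**Working it through.** The plan gives no SD, correlation, power or sample-size derivation, so there is no figure to reproduce.

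**Inputs**

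- From the documents: N = 75 and 2:1 allocation, hence 50 and 25.
- Assumed: two-sided 95% interval; complete data; entry SD s = 12 mm Hg (it cancels from the ratios); entry-to-follow-up correlation r = 0.3 to 0.8, with 0.5 to 0.7 as the central range; k = follow-up SD / entry SD = 0.8, 1 or 1.2.

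**Formulas (change from entry)**

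- Var(change) = s²(1 + k² − 2rk), 73 df.
- Var(adjusted) = s²k²(1 − r²), 72 df, times 1 + 1/71 = 1.0141 for estimating the slope.
- Standard-error factor: √(1/50 + 1/25) = 0.245.
- t quantiles: 1.9930 (73 df) and 1.9935 (72 df).

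**Example, k = 1, r = 0.5**

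- Change score: Var = 144 × 1 = 144; half-width 1.9930 × 12 × 0.245 = 5.86 mm Hg.
- Adjusted: Var = 144 × 0.75 = 108; half-width 1.9935 × √(108 × 1.0141) × 0.245 = 5.11 mm Hg.
- Ratio 5.11 / 5.86 = 0.872, or 13% narrower.

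**Width ratio, adjusted / change score**

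| r | k = 0.8 | k = 1 | k = 1.2 |
|---|---|---|---|
| 0.3 | 0.714 | 0.812 | 0.879 |
| 0.5 | 0.761 | 0.872 | 0.940 |
| 0.6 | 0.782 | 0.901 | 0.967 |
| 0.7 | 0.798 | 0.929 | 0.990 |
| 0.8 | 0.806 | 0.956 | 1.006 |

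The worst case is rk = 1, where the true slope is already 1 and adjustment can only cost its degree of freedom. At k = 1.43, r = 0.7 the ratio is 1.007.

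**Half-widths at s = 12 mm Hg**

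- k = 1: 5.86 to 5.11 (r = 0.5); 4.54 to 4.21 (r = 0.7).
- k = 1.2: 6.52 to 6.13 (r = 0.5); 5.11 to 5.06 (r = 0.7).

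**Checks**

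- With an assumed 20% loss (40 versus 20) and k = 1, the ratios are 0.874 (r = 0.5) and 0.930 (r = 0.7).
- Simulation of 20,000 trials at 50:25 gave mean ratios of 0.873 and 0.929 (k = 1, r = 0.5 and 0.7) and 0.940 and 0.990 (k = 1.2). The mean error of either estimator was at most 0.03 mm Hg.
- A separate simulation (4,000 trials per r, k = 1) gave coverage of about 95% for both methods.
- Mixed model with five assumed visits (months 0, 3, 6, 9, 12), categorical time, equal correlations and known covariance: constraining the entry means rather than leaving them free gives ratios of 0.866 (r = 0.5) and 0.922 (r = 0.7) for month 12 minus entry.

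**The other reading: month 12 minus month 3**

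With equal SDs, entry SBP explains a share (r₀₁₂ − r₀₃)² / [2(1 − r₃₁₂)] of the variance of this difference, where r₀₃, r₃₁₂ and r₀₁₂ are the correlations entry–month 3, month 3–month 12 and entry–month 12.

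| r₀₃ / r₃₁₂ / r₀₁₂ | Width ratio |
|---|---|
| 0.6 / 0.6 / 0.6 | 1.007 |
| 0.7 / 0.6 / 0.5 | 0.982 |
| 0.7 / 0.7 / 0.5 | 0.973 |
| 0.6 / 0.7 / 0.5 | 0.999 |
| 0.5 / 0.5 / 0.3 | 0.987 |

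In the five-visit model, constraining the entry means leaves the variance of this contrast unchanged (ratio 1.000).

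**The case against.** The strongest reply is that this is a pilot with descriptive feasibility outcomes as primary. The planned analysis is valid, no power or precision target is stated that it could miss, and the interval stays wide either way. The gain also depends on a reading the text does not confirm and on inputs the documents do not give. All of that is true, and it sets the severity low. It does not remove the undefined reference visit, or the fact that a usually tighter estimate is available at almost no cost.

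A second objection concerns k. Under Study Design some patients enter because their BP is raised, and the upper exclusion trims the other end. Selecting on entry SBP shrinks its SD and pushes k above 1. Starting from k = 1 and r = 0.5 to 0.7 before selection, an entry SD reduced to 0.8 of its value leaves a gain of about 5 to 9%; reduced to 0.6, about 2 to 5%. How many patients enter this way is unknown, and patients entering on treatment have no stated lower BP limit. So this gives a direction, within the range tabulated above, and it is a reason not to rely on 7 to 13% alone.

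Third, the BP used for eligibility need not be an office reading taken as at follow-up. That stands as a condition: the value has to be recorded as baseline office SBP. The plan also does not say whether the mixed model leaves the entry means free; if it already constrains them, stating so would settle that part.

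Finally, controls wear the tracker from month 6, so a 12-month contrast is not tracker versus no tracker. That is a separate and larger matter, which baseline adjustment does not address.

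**Conclusion.** The point holds, at low severity. The reference visit for change is unclear and no baseline SBP term is stated; neither statement needs an assumed input.

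The gain is conditional. If change is from entry, with equal SDs and r of 0.5 to 0.7, adjustment narrows the 95% interval by about 7 to 13% (4 to 19% for r of 0.8 to 0.3). With a follow-up SD 1.2 times the entry SD the gain is 1 to 6% for r of 0.7 to 0.5, and at r = 0.8 the interval is 0.6% wider. With an SD ratio of 0.8 the gain is 20 to 24% for r of 0.7 to 0.5. The largest loss is about 0.7%. If change is month 12 minus month 3, the width ratio is about 0.97 to 1.01, so there is next to nothing to gain.

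The SDs, the correlations and complete data are all assumptions. The comparison is unbiased under randomisation with or without adjustment.

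**What to change.** Two separate decisions.

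1. **Outcome definition.** State the reference visit for change in one sentence, noting that entry is the pre-randomisation reference and that month 3 is not. Agree this before anyone reviews BP data by arm, so that the choice cannot depend on the results.
2. **Analysis, if the reference is entry.** Estimate the arm difference in office SBP at each follow-up visit by ANCOVA on entry SBP, or by a mixed model with categorical time and either entry SBP as a covariate or entry means constrained equal across arms, but not both. Report it with a 95% CI in place of the unadjusted t-test.

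Record the eligibility-visit office SBP as the baseline value, and add a BP row to the visit schedule.

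The first decision clarifies or changes the outcome definition. The second takes one or two sentences and one degree of freedom (73 to 72), at a cost of about 0.7% of interval width if entry SBP adds nothing. No new measurement is needed, provided the entry BP used for eligibility is recorded as baseline office SBP. If the sponsor keeps month 12 minus month 3, only the first decision matters.
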